12.8.2 Power for analysis of selected secondary variables

The following test of secondary variables are part of the global testing strategy.

Page 59 of 63 Protocol No. CLCZ696BCN04

For the paired differences of numbers of NSVT, SVT, ICD shocks and ATP over ACEI/ARB and ARNI treatment period, the above sample size will provide >95% power to detect mean of paired difference of at least -3 and standard deviation of at most 10. These are under the assumption of similar patient experiences as de Diego et al (2018)'s study.

For the change from date of treatment initiation after 6 months of treatment assessed by LVEF and NT-proBNP, the above sample size will provide 84% – 91% power to detect a treatment difference of 3 numeric values at the two-sided significance level of 0.05, assuming a standard deviation of 15.

13 Ethical considerations and administrative procedures

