12.8 Sample size calculation

12.8.1 Primary endpoint

McNemar Test is used in the primary analysis to test for 2 correlated proportions. Approximate formula from Machin et al (1997) is used to calculate the minimum size required.

For the proportion of discordant pairs, the following approximate formula is used:

Proportion Discordant =
$$P_t(1 - P_s) + P_s(1 - P_t)$$

where P_t and P_s are proportion of patients experiencing the event of interest during ACEI/ARB and ARNI treatment period respectively. Over here, both proportions are assumed to be similar to de Diego et al (2018)'s study. According to de Diego et al (2018)'s study, SVT (one of the VA event) has the following incidence 8/120 and 1/120 during ACEI/ARB and ARNI treatment period respectively. Hence, by substitute both into the equation above, proportion discordant calculated is 0.0739 after rounding off.

For the difference, a parameter under effect size is approximated by the following formula:

Effect Size =
$$P_t(1 - P_s) - P_s(1 - P_t)$$

and after substituting P_t and P_s defined above, the effect size calculated is -0.0583.

Thus, by considering the parameters defined above, power of 0.8 and significance level of 0.05, the sample size required is 175. Further consider a dropout rate of 20%, the minimum sample size required is 219.

The above calculation is calculated using PASS 11 software's Test for Two Correlated Proportion (McNemar Test) [Differences] procedure.

For proportion of patients had ICD or CRT-D shocks occurrence over 6 months of ACEI/ARB and 6 months of ARNI treatment, the above sample size will provide 95% - 98% power to detect a proportion difference of 0.075 at two-sided significance level of 0.05. The proportion difference is derived from the published literature (de Diego et al 2018).

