7.1 Overall Statistical Considerations

All statistical analyses are performed using SAS9.4.

All subjects related, efficacy related and safety related data should be collected and included in the statistical analysis. Notes or descriptive text records are only listed. For other data, descriptive statistical analysis would be performed, also statistical inference would be applied if needed.

In the statistical tabulations, screening number of subjects is the universal unique identifier of subjects in the study.

General rules of descriptive statistics: Quantitative variables are described by mean, standard deviation, standard error, median, minimum, maximum, Q1 and Q3. Categorical variables are

described by number and percentage of each category. Two-sided 95% confidence intervals will also be calculated for efficacy endpoints.

In the laboratory test part and the efficacy analysis part, 2 digits will be retained for the upper and lower limits of means and their confidence intervals, 3 digits for standard deviations, and 2 digits for medians, minimums, maximums, Q1 and Q3. In other parts, 1 digit more than the original values can be retained for the upper and lower limits of means and their confidence intervals, 2 digits more for standard deviations, and the original value digits for medians, minimums, maximums, Q1 and Q3. One decimal place will be retained for percentages and the upper and lower limits of their confidence intervals (but for efficacy analysis, 2 decimal places will be retained).

General principles of statistical inference: paired t test and Wilcoxon rank sum test will be used to compare quantitative data. McNemar test, exact test (binomial sign test) and Liddell's exact test will be used to compare categorical variables. All statistical tests will be subjected to twosided tests (unless otherwise specified), and a P-value less than or equal to 0.05 will be considered to indicate a statistically significant difference (unless otherwise specified).

For values such as "< xxx", half of the number following the less-than sign will be used to summarize and calculate statistics. For values such as "> xxx", xxx will be used to summarize and calculate statistics. For values such as "xx-xx", the average of the numbers before and after "-" will be used to summarize and calculate statistics. P value is rounded to 4 decimal places. If P < 0.0001, it is presented as '< .0001'; if P > 0.9999, it is presented as '> .9999'.

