7.4.2 Efficacy analysis of secondary endpoints

The analysis will be based on the efficacy analysis set and the per protocol set.

- Paired numbers of VA (SVT and NSVT in separate), PVC, ICD or CRT-D shocks and ATP over 6 months of ACEI/ARB treatment and 6 months of ARNI treatment.
- Change in LVEF from date of treatment initiation over 6 months of ACEI/ARB treatment and 6 months of ARNI treatment.
- Change of NYHA level over 6 months of ACEI/ARB treatment and 6 months of ARNI treatment.
- Change proportion of NT-proBNP from date of treatment initiation over 6 months of ACEI/ARB treatment and 6 months of ARNI treatment.
- Number of hospitalizations for all causes and HF related hospitalizations during ACEI/ARB and ARNI treatments.
- Paired numbers of VA (SVT and NSVT in separate), PVC, ICD or CRT-D shocks and ATP over 3 months of ACEI/ARB treatment and 3 months of ARNI treatment.
- Number of hospitalizations for all causes and HF related hospitalizations during 3 months of ACEI/ARB and ARNI treatments.

Analysis of change from date of treatment initiation after 6 months of treatment (for paired quantitative endpoints)

Variables involved are number of SVT experienced, number of NSVT experienced, number of hourly PVC experienced, number of ICD or CRT-D shocks experienced, number of ATP experienced and time duration of NSVT experienced, as well as number of hospitalizations for

all causes and HF related hospitalizations.

The number of occurrences or duration of each variable within 3 months and 6 months and their changes from baseline will be descriptively analyzed by treatment group and compared between groups. The changes will be summarized by mean, standard error, median, quartiles, minimum and maximum. Because the baseline and post-treatment device data collection cycles are different, data will be standardized on a daily basis before the analysis of changes.

Normality will be checked for the values of each variable and changes calculated. If the data is parametric, paired t-tests will be performed; else if the data is non-parametric, Wilcoxon signed-rank test will be used.

Analysis of change from date of treatment initiation after 6 months of treatment (for continuous endpoints)

[figure not shown]
Variables involved are LVEF, NYHA and NT-proBNP.

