The values of each variable at visits following 3 months and 6 months of treatment and their changes from baseline will be descriptively analyzed by treatment group and compared between groups. The changes will be summarized by mean, standard error, median, quartiles, minimum and maximum.

Normality will be checked for the values of each variable and changes calculated. If the data is parametric, paired t-tests will be performed; else if the data is non-parametric, Wilcoxon signed-rank test will be used.

NYHA is a qualitative variable, and NYHA level will be subject to Ridit transformation into a numerical Ridit value before the above analysis is carried out. The basic idea of Ridit transformation is to first determine a standard group (the sum of the frequencies of each treatment group of each grade is taken as the standard group), and then obtain the Ridit value R of each grade of the standard group. The weighted average of the frequency of each grade in each group and the R value of each grade in the standard group will be respectively used to obtain the average Ridit value of each group, and then compare between groups.

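### Six secondary tests are assigned to a global testing strategy that the visible text never defines, while the SAP calls any two-sided P ≤ 0.05 significant

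*Protocol*

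**What the plan says.** Protocol 12.8.2 and SAP 3.2.2 carry the same opening sentence: "The following test of secondary variables are part of the global testing strategy". Two power statements follow. The first covers paired differences in the numbers of NSVT, SVT, ICD shocks and ATP (mean difference 3 in size, SD 10, power above 95%). The second covers LVEF and NT-proBNP (difference 3, SD 15, two-sided 0.05, power 84% to 91%). That makes six variables.

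The only decision rule that visibly applies to these tests is in SAP 7.1. It says "All statistical tests will be subjected to twosided tests (unless otherwise specified") and that "a P-value less than or equal to 0.05 will be considered to indicate a statistically significant difference", with the same proviso. Nothing visible specifies otherwise for a secondary test.

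SAP 7.4.2 analyses 11 variables. Eight are paired quantities: SVT, NSVT, hourly PVC, shocks, ATP, NSVT duration, all-cause hospitalisations and HF hospitalisations. Three are treated as continuous: LVEF, NYHA and NT-proBNP. For both groups it states "Normality will be checked for the values of each variable and changes calculated" and then applies a paired t-test or a signed-rank test. For the continuous group it adds "The values of each variable at visits following 3 months and 6 months of treatment and their changes from baseline will be descriptively analyzed", and it also compares the treatments. All of this is done in the efficacy analysis set and again in the per-protocol set.

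**The concern.** A reader who meets the phrase global testing strategy will take it that the secondary tests are protected by a hierarchy, a gate or an alpha allocation. None can be found in Protocol 12.4, 12.5, 12.7 or 12.8, or in SAP 3.2, 5, 7.1 or 7.4. SAP 5 refers the hypotheses to 7.4, and 7.4 is silent on multiplicity.

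Followed as written, any of the six tests with P ≤ 0.05 is declared significant whatever the primary result, and the report can say that it came from a global strategy. This is an open-label, single-arm study with sequential treatment periods. An isolated LVEF or NT-proBNP result could then be presented as a confirmed ARNI benefit without the error control that the phrase implies.

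**Working it through.** **1. The plan's own power figures.** Power for a paired difference is Φ(δ/SD × √n − 1.96), with n = 175 evaluable or 219 enrolled (Protocol 12.8.1).

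- Event counts, 3/10: at n = 175, Φ(0.3 × 13.23 − 1.96) = 97.8%; at n = 219, 99.3%. The stated figure of above 95% reproduces at an unadjusted two-sided 0.05.
- LVEF and NT-proBNP, 3/15: at n = 175, Φ(0.2 × 13.23 − 1.96) = 75.4%; at n = 219, 84.1%. The lower stated figure of 84% reproduces at 219. The upper figure of 91% appears only at n = 275, the superseded sample size in the amendment log. That is a separate matter.

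The quoted powers thus use the full 0.05 for each test. An equal split over six tests (0.05/6 = 0.0083) would give 90.2% for the counts at n = 175 and 61.7% for LVEF and NT-proBNP at n = 219, so no such split is built in. A fixed testing order would also leave each test at 0.05, so this alone does not rule out a strategy. The point rests on the absence of any stated one.

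**2. Number of tests.**

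- Introduced by the sentence itself: 4 counts + LVEF + NT-proBNP = 6.
- Named for analysis in SAP 7.4.2: 8 + 3 = 11, with one test per variable.

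**3. Chance of at least one false claim.** Assume that no secondary effect exists and that each test is two-sided at 0.05. For k independent tests the chance is 1 − 0.95^k: for k = 6, 1 − 0.7351 = 0.265; for k = 11, 1 − 0.5688 = 0.431. For correlated tests I used normal test statistics with a common correlation. The documents give no correlations, so these are assumptions shown as a range.

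| Tests | Correlation 0 | 0.3 | 0.5 | 0.8 |
|---|---|---|---|---|
| 6 (sentence as written) | 0.26 | 0.24 | 0.21 | 0.14 |
| 11 (all variables, one test each) | 0.43 | 0.37 | 0.30 | 0.18 |

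The lowest figure, 0.14, is 2.8 times 0.05. Testing both values and changes, and adding the 3-month versions, raises the rate further.

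**The case against.** The strongest reply is that the sentence is narrow and the plan is modest. The section heading speaks of selected secondary variables, and only six follow. Protocol 2 says that the study aims to explore effects, Protocol 12.4 uses the same verb for the primary objective, and Protocol 2.2 lists no secondary estimands. A Phase IV study may leave its secondary tests uncontrolled. All of this stands, and it limits the size of the point. It does not remove it: an exploratory study should not describe its secondary tests as part of a testing strategy and also call each P ≤ 0.05 significant.

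Three stronger readings are tempting, and the documents do not support them.

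- **That the strategy covers some 40 tests.** A reader could count values and changes at 3 and 6 months: 9 variables × 2 × 2, plus LVEF and NT-proBNP × 2 at 6 months only (Protocol Table 8-1 has no Month 3 or 9 echocardiogram or NT-proBNP), which is 36 + 4 = 40. The false-claim chance would be 0.57 at correlation 0.5 (0.87 at 0, 0.28 at 0.8). The arithmetic is sound, but it treats every version as an equal claim. The sentence does not reach PVC, NSVT duration, NYHA or hospitalisations, and NSVT duration is in no endpoint list.
- **That no set, time point or contrast is named.** SAP 6 makes the efficacy analysis set the primary population for efficacy. The Protocol 12.5.1 endpoints are framed over 6 months of each treatment, and both analysis headings in SAP 7.4.2 refer to 6 months. The endpoint lists name paired numbers for events, change for LVEF and NYHA, and change proportion for NT-proBNP.
- **That no strategy exists at all.** Protocol 12.6 and the SAP contents entries after 7.4.2 are blank in the public text, and the SAP 7.1 rule carries its proviso. A rule in text not shown cannot be excluded.

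**Conclusion.** The concern holds for the six variables. Both documents claim a global testing strategy for them, the visible text defines none, and the only operative rule is significance at two-sided 0.05 for each test. The chance of at least one false claim is about 0.21 at correlation 0.5 (0.26 at 0, 0.14 at 0.8). It is about 0.30 (0.43 to 0.18) if all 11 variables of SAP 7.4.2 are read the same way. These figures assume that every null hypothesis is true, one test per variable, and correlations that I have chosen. The point concerns the secondary tests only, not the five primary endpoints. It is a defect in what the plan claims and in how results may be labelled. It does not alter the primary analysis or the sample size.

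**What to change.** First check whether the text not shown defines a strategy. If it does, cite it in Protocol 12.8.2 and SAP 3.2.2. If it does not:

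1. Delete the sentence on the global testing strategy from both sections.
2. In SAP 7.1, limit the P ≤ 0.05 significance rule to the primary analysis.
3. In SAP 7.4.2, state that all secondary P values, including the 3-month and per-protocol tests, are nominal and exploratory and support no confirmatory claim.

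A gated secondary family, such as a Holm procedure opened by primary success, should not be added unless a primary success rule is stated first. The plan shows none for its five primary endpoints, so the gate would have nothing to act on.

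The cost is wording in four sections, with no new data or patients. The sponsor gives up calling an isolated secondary P ≤ 0.05 statistically significant.

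### The >95% power stated for SVT counts rests on a mean and SD that cannot occur together at the plan's own SVT rates, so the figure is unsupported for SVT

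*Protocol*

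**What the plan says.** Protocol 12.8.2 makes one power statement for four event counts. Its scope is "For the paired differences of numbers of NSVT, SVT, ICD shocks and ATP over ACEI/ARB and ARNI treatment period", and the claim is that the sample size "will provide >95% power to detect mean of paired difference of at least -3 and standard deviation of at most 10". The source follows: "These are under the assumption of similar patient experiences" to the cited 120-patient study. SAP 3.2.2 repeats the statement.

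Protocol 12.8.1 uses the same study for the primary sample size: "SVT (one of the VA event) has the following incidence 8/120 and 1/120 during ACEI/ARB and ARNI treatment period respectively". Treating the two periods as independent, it reports that the "proportion discordant calculated is 0.0739 after rounding off". The size follows from "power of 0.8 and significance level of 0.05, the sample size required is 175" and then "Further consider a dropout rate of 20%, the minimum sample size required is 219".

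Protocol 12.5.2 and SAP 7.4.2 analyse the counts with a paired t-test if a normality check is passed; "else if the data is non-parametric, Wilcoxon signed-rank test will be used". Neither document gives the number of SVT episodes per affected patient.

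**The concern.** Two planning statements draw on one prior study and do not fit together for SVT. If almost all patients have no SVT in either period, almost all paired differences are zero. A mean difference of 3 across all patients must then come from a few very large differences, and those inflate the SD. The question is whether an SD of 10 or less is still possible.

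SVT is the event that sized the trial, and Protocol 12.8.2 places these secondary tests in the global testing strategy. If the SVT count shows no difference, a reader who trusts a power above 95% will take that as strong evidence of no effect. The plan has not shown that the design supports that reading.

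**Working it through.** **Inputs.** Mean 3 in absolute value, SD 10 (Protocol 12.8.2); SVT in 8/120 and 1/120 (12.8.1); n = 175 evaluable and 219 enrolled (12.8.1), since the power statement does not say which it means; two-sided 0.05 (SAP 7.1).

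**1. Reproducing the stated power.** For a paired t-test the noncentrality is (3/10)·√n. This gives 97.7% at 175 and 99.3% at 219. So the >95% follows from mean 3 and SD 10 by normal theory.

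**2. Can mean 3 and SD at most 10 occur for SVT?** If a share q of patients has a non-zero difference, the Cauchy-Schwarz inequality gives SD ≥ |mean|·√(1/q − 1), whatever the shape of the counts.

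| Share used | q | Minimum SD at mean 3 |
|---|---|---|
| Largest possible non-zero share, (8+1)/120 | 0.075 | 3·√12.33 = 10.5 |
| The plan's discordant share | 0.0739 | 3·√12.53 = 10.6 |
| Favourable differences only, 8/120 | 0.0667 | 3·√14 = 11.2 |

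The last row is the stricter bound. Only patients with SVT on ACEI/ARB can have fewer episodes on ARNI, so the mean square is at least 9/(8/120) = 135, the variance at least 135 − 9 = 126, and the SD at least 11.2. Every bound exceeds 10. A larger mean raises the bound in proportion, so it does not help.

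**3. Which test would be used.** Under the plan's independence formula:
- SVT on ACEI/ARB only: (8/120)(119/120) = 0.0661
- SVT on ARNI only: (1/120)(112/120) = 0.0078
- Total 0.0739, of which 0.0661/0.0739 = 89.5% favours ARNI.

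About 93% of differences are zero, so a normality check will almost certainly fail. The signed-rank test then rests on 175 × 0.0739 = 12.9 non-zero pairs, or 16.2 at 219. (SAP 7.1 names a rank sum test in its general principles; I use the specific rule in SAP 7.4.2, which agrees with Protocol 12.5.2.)

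**4. Signed-rank power.** Method: number of non-zero pairs ~ Binomial(n, 0.0739), zeros dropped, exact null distribution. The result depends on n, the split of directions and the relative sizes of the differences; the mean of 3 itself does not enter.

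| Assumption on sizes | n = 175 | n = 219 |
|---|---|---|
| Similar in both directions | 77.9% | 87.0% |
| ARNI-only differences small | 97% | 99% |
| ARNI-only about half as large | 87% | 94% |
| ARNI-only ten times as large | 54% | 63% |

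The ten-fold row is a normal approximation and a stress case: 0.0661 − 10 × 0.0078 is negative, so the mean would turn against ARNI. Low power does not need that reversal, because only rank order matters. If every ARNI-only difference is slightly larger than every ACEI/ARB-only one, say by 10%, a mean of 3 in favour of ARNI is still possible, with about 3/(0.0661 − 1.1 × 0.0078) = 52 episodes per ACEI/ARB-only patient. I ran the exact calculation with the ARNI-only pairs given the top ranks; it gives 51% at 175.

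Other variations at 175 with similar sizes: no patient with SVT in both periods, 76.9%; zeros kept in the ranking (normal approximation), about 87%. If 7/120 of patients have a non-zero difference and all of these are favourable, power is 94.6%.

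**The case against.** The strongest reply is that the sentence is conditional: given mean 3 and SD 10, power exceeds 95%. That arithmetic is right. The impossibility alone also costs little. At the minimum SDs of 10.5 to 10.6, nominal paired-t power is still about 96% at 175 and 99% at 219; at 11.2 it is 94.0% and 97.6%. The lower values come from a separate argument, about the test and the shape of the counts. The study rates are themselves estimates, and the sample size rests on the McNemar calculation, not on this sentence.

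Most of this stands and limits the point. It does not rescue the statement for SVT: the plan names SVT, ties the inputs to the cited study, and takes from that study rates at which the inputs cannot occur.

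Three stronger readings are tempting, and the documents support none of them.
- **SVT power is 78%.** That figure needs similar episode counts in both directions, which neither document states. With small ARNI-only counts the signed-rank test reaches 97%.
- **The other counts fail too.** The documents give no per-period rates for NSVT, ATP or shocks (for shocks only a difference of 0.075), so nothing is shown for them.
- **A count with more than 8.3% of patients affected may keep the >95%.** The share 9/(9 + 100) = 8.3% only makes mean 3 with SD 10 possible. In the similar-size signed-rank model it gives about 83% at 175 and 91% at 219.

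**Conclusion.** Wrong as written, for SVT only. At 8/120 and 1/120, a mean paired difference of 3 needs an SD of at least 10.5, and at least 11.2 on the stricter bound. This uses only the plan's own rates and no assumption about the distribution of counts. The >95% is therefore unsupported for SVT; it is not disproved.

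The replacement figures rest on more: the plan's independence formula, the signed-rank test with zeros dropped, and a stated assumption on relative episode counts. With similar counts in both directions, power is about 78% at 175 and 87% at 219. The range of about 54% to 97% at 175 describes the scenarios in the first table of step 4, and its low end is not a floor.

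**What to change.** In Protocol 12.8.2 and SAP 3.2.2, take SVT out of the sentence that claims more than 95% power. Add a separate statement for the SVT count covering:
- the test (Wilcoxon signed-rank) and the rates (8/120 and 1/120, periods independent);
- power of about 78% at 175 evaluable patients and 87% at 219, if episode counts per affected patient are similar in both directions;
- about 54% to 97% at 175 if they are not, with the scenarios named.

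Do not make a minimum affected share of 8.3% the condition for keeping the >95% claim for the other counts.

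The cost is one changed sentence and one added statement in each document, and a less favourable figure for SVT. No patients, visits or analyses are added.

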1.2 Purpose

The purpose of this study is to generate effectiveness data of ARNI, in the Chinese HFrEF patients with implanted ICD or CRT-D.

2 Objectives and endpoints

This study aims to explore the effect of ARNI on VA and ICD or CRT-D shocks and ATP. The objectives and related endpoints are further described in Table 2-1.

Table 2-1 Objectives and related endpoints

Objectives	Endpoints			
Primary Objective	Endpoint for primary objective			
To assess the proportion of patients with VA events over 6 months of ACEI/ARB and 6 months of ARNI treatment	Proportion of patients with VA events over 6 months of ACEI/ARB and 6 months of ARNI treatment (VA events are defined as SVT, NSVT and PVC, ICD shock and ATP, the definitions of SVT, NSVT, PVC, ATP are as below)			

Ok	pjectives	Endpoints			
Se	condary Objectives	Endpoints for secondary objectives			
•	To assess the number of occurrences of VA events and ICD or CRT-D shocks over 6 months of ACEI/ARB and 6 months of ARNI treatment	Numbers of NSVT, SVT, PVC, ICD shock and ATP experienced by patients over 6 months of ACEI/ARB and 6 months of ARNI treatment			
•	To compare the changes in LVEF and NYHA level between ACEI/ARB and ARNI treatments	 LVEF (%) over 6 months of ACEI/ARB and 6 months of ARNI treatment NYHA level over 6 months of ACEI/ARB and 6 months of ARNI treatment 			
•	To compare the changes in the NT-proBNP level between ACEI/ARB and ARNI treatments	NT-proBNP (pg/mL) level over 6 months of ACEI/ARB and 6 months of ARNI treatment			
•	To compare the healthcare resource utilization of HF patients during ACEI/ARB and ARNI treatments	Number of hospitalizations for arrhythmia or HF related hospitalizations over 6 months of ACEI/ARB and 6 months of ARNI treatment			

Abbreviations: ACEI = angiotensin-converting enzyme inhibitor;

; ARB = angiotensin receptor blockers; ARNI = angiotensin receptor neprilysin inhibitor; ATP = anti-tachycardia pacing; CRT-D = cardiac resynchronization therapy-defibrillator; HF = heart failure; ICD = implantable cardioverter defibrillator; LVEF = left ventricular ejection fraction; NSVT = non-sustained ventricular tachycardia; NT-proBNP = N-Terminal prohormone of Brain Natriuretic Peptide; NYHA = New York Heart Association; PVC = premature ventricular contraction; SVT = sustained ventricular tachycardia; VA = ventricular arrhythmias

Note

Sustained ventricular tachycardia is defined as tachycardia with hemodynamic disorder or lasting for >30 seconds

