12.5 Analysis of secondary endpoints

12.5.1 Efficacy endpoints

Please refer to Section 2 for the secondary objectives. The corresponding secondary variables are listed below:

- 1. Paired numbers of VA (SVT and NSVT in separate), PVC, ICD and ATP over 6 months of ACEI/ARB treatment and 6 months of ARNI treatment
- 2. Change in LVEF from date of treatment initiation over 6 months of ACEI/ARB treatment and 6 months of ARNI treatment
- 3. Change of NYHA level over 6 months of ACEI/ARB treatment and 6 months of ARNI treatment
- 4. Change proportion of NT-proBNP from date of treatment initiation over 6 months of ACEI/ARB treatment and 6 months of ARNI treatment
- 5. Number of hospitalizations for all causes and HF related hospitalizations during ACEI/ARB and ARNI treatments

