3.2.2 Power for analysis of selected secondary variables

The following test of secondary variables are part of the global testing strategy.

For the paired differences of numbers of NSVT, SVT, ICD shocks and ATP over ACEI/ARB and ARNI treatment period, the above sample size will provide >95% power to detect mean of paired difference of at least -3 and standard deviation of at most 10. These are under the assumption of similar patient experiences as de Diego et al (2018)'s study.

For the change from date of treatment initiation after 6 months of treatment assessed by LVEF and NT-proBNP, the above sample size will provide 84% - 91% power to detect a treatment difference of 3 numeric values at the two-sided significance level of 0.05, assuming a standard deviation of 15.

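### The 84–91% power stated for LVEF and NT-proBNP has no NT-proBNP scale, SD or source behind it, and at the current sample size its own inputs give about 75–84%

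*Protocol*

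**What the plan says.** Protocol 12.8.2 describes its secondary tests as part of a global testing strategy. For the change over six months of treatment, it covers two variables in one sentence: "assessed by LVEF and NT-proBNP, the above sample size will provide 84% – 91% power to detect a treatment difference of 3 numeric values". The assumption attached is "at the two-sided significance level of 0.05, assuming a standard deviation of 15". SAP 3.2.2 repeats it: "treatment difference of 3 numeric values at the two-sided significance level of 0.05, assuming a standard deviation of 15". No unit or source follows either number in either document.

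The two variables are on different scales. Protocol Table 2-1 gives LVEF in % and lists "NT-proBNP (pg/mL) level over 6 months of ACEI/ARB and 6 months of ARNI treatment"; Protocol 8.3.2 and SAP 4.1.2 also use pg/mL. Protocol 12.5.1 lists the NT-proBNP variable as "Change proportion of NT-proBNP from date of treatment initiation over 6 months of ACEI/ARB treatment and 6 months of ARNI treatment", as does SAP 7.4.2. The methods text (Protocol 12.5.2, SAP 7.4.2) then takes simple differences or changes from baseline and tests them with a paired t-test, or a Wilcoxon signed-rank test if they are not normal.

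The sample size in Protocol 12.8.1 is 175, raised to 219 for 20% dropout. Before Amendment 2 it was 275.

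**The concern.** Power depends on the ratio of effect to SD, and both must refer to the same variable on the same scale. One unit-free pair is used here for a percentage and for a concentration that the plan also treats as a proportion. A reader cannot tell what 3 and 15 mean for NT-proBNP, or check them.

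The range is also attached to the current sample size, although Amendment 2 cut enrolment from 275 to 219. A power range calculated for 275 should have fallen.

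Comparing NT-proBNP between treatments is a named secondary objective. If the result is not significant, a stated power of at least 84% invites the reading that a well-powered comparison found nothing. For NT-proBNP the documents give no basis for that reading; for LVEF they overstate it.

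**Working it through.** **Inputs.** Effect 3, SD 15 and two-sided 0.05 (Protocol 12.8.2); 175 evaluable and 219 enrolled (Protocol 12.8.1); paired t-test (Protocol 12.5.2). Assumption: 15 is the SD of the within-patient paired difference, which the text does not say. The 275 in the amendment log is used only to trace where the range came from; with 20% dropout it leaves 275 × 0.80 = 220.

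**Attempt to reproduce 84–91%.** Noncentrality = (3/15) × √n = 0.2√n, with n − 1 degrees of freedom. The normal approximation is Φ(0.2√n − 1.960).

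| n | 0.2√n | Normal approximation | Noncentral t |
|---|---|---|---|
| 175 (current, evaluable) | 2.646 | Φ(0.686) = 75.4% | 74.9% |
| 219 (current, enrolled) | 2.960 | Φ(1.000) = 84.1% | 83.8% |
| 220 (superseded, evaluable) | 2.966 | Φ(1.006) = 84.3% | 84.0% |
| 275 (superseded, enrolled) | 3.317 | Φ(1.357) = 91.3% | 91.1% |

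The current sizes give 75–84%. The stated range matches the last two rows. Solving for n gives the same answer: 84% needs [(1.960 + 0.994) × 5]² ≈ 218 pairs, and 91% needs [(1.960 + 1.341) × 5]² ≈ 272.

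**Other readings of the inputs.**
- One-sided 0.05: 83.9% at 175 and 90.4% at 219. The text says two-sided.
- Two independent samples: 46% and 55%.
- SD 15 within each period with a correlation of 0.6: the SD of the difference is 15 × √(2 × 0.4) = 13.4, giving 83.7% and 90.9%. The documents state no correlation.

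**NT-proBNP, scale by scale.**
- pg/mL: 84% power for a difference of 3 needs a paired-difference SD of at most 3√n/2.954, which is 13.4 pg/mL at 175 and 15.0 pg/mL at 219. No NT-proBNP SD is given to compare with this.
- Proportion: 3 would be a difference of 300% in relative change.
- Percentage points of change: 3 and 15 are arithmetically possible, but the text neither says this nor gives a source.

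**How far power depends on the missing SD.** The SDs below are assumptions; the documents give none. The effect is 3 on the same scale.

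| Assumed paired SD | Power, n = 175 | Power, n = 219 |
|---|---|---|
| 15 | 74.9% | 83.8% |
| 30 | 26.0% | 31.4% |
| 50 | 12.4% | 14.3% |
| 100 | 6.8% | 7.3% |
| 500 | 5.1% | 5.1% |

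Whatever the scale, the difference detectable with 80% power is (1.960 + 0.842) × SD/√n, or 0.21 SD at 175 and 0.19 SD at 219.

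**The case against.** The strongest defence is that the plan defines the NT-proBNP variable as a proportional change. Expressed in percent, 3 and 15 become percentage points, and one pair could in principle serve both measures. This stands in part: the difference in units does not make the inputs impossible. It does not supply the missing scale, SD or source, and Table 2-1 still gives pg/mL.

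A second defence is that SD 15 may be a per-period SD. The neighbouring paragraph on event counts speaks of a paired difference, whereas this one says only "assuming a standard deviation of 15". With a correlation of 0.6 the range would reproduce at 175–219. That correlation appears nowhere in the documents, whereas 220 and 275 reproduce the range with no added input. The ambiguity is real, and it is a reason to state which SD is meant.

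These are also secondary endpoints, and the target of 219 comes from the McNemar calculation on sustained ventricular tachycardia. That stands.

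Some stronger readings go too far. A reader might infer that 15 was borrowed from LVEF; no passage says so, and it is unsourced for LVEF as well. A reader might also take the low powers in the second table as the true NT-proBNP power, but they rest on assumed SDs and show only how much depends on the missing figure. Nor do the documents link this input to the interim re-evaluation of sample size: Protocol 4.5 and SAP 3.4 refer to the minimum required size, which Protocol 12.8.1 derives from the primary endpoint.

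**Conclusion.** The point holds in two parts.

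1. The NT-proBNP power claim is unsupported. The effect and SD have no unit or source, the documents use two different scales for the variable, and they give no SD on either. The claim cannot be confirmed, and the true power cannot be calculated from the documents.
2. With 15 read as the SD of the paired difference, the stated range is too high at the current size for either variable: about 75% at 175 and 84% at 219, against 84–91%. The upper end is overstated by about 7 percentage points (91 − 84) and the lower by about 9 (84 − 75). That the range was carried over from the 275-patient version is the simplest explanation, but it is an inference from the match.

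Neither part shows that 219 is wrong or affects the primary analysis.

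**What to change.** Make the same changes in Protocol 12.8.2 and SAP 3.2.2.

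- **NT-proBNP.** Take it out of the sentence. Either state that no power is claimed for it, or give it a separate sentence with its own effect, SD, scale and source. First reconcile pg/mL (Table 2-1) with proportional change (Protocol 12.5.1, SAP 7.4.2), so that the power statement describes the analysis that will be run. Power on a scale the plan does not use, such as log ratios, would need the planned analysis to change too.
- **LVEF.** Do not keep 84–91%. Give the unit (percentage points), say that 15 is the SD of the paired difference and cite its source, and restate power as about 75% with 175 pairs and 84% with 219. If the sponsor meant a per-period SD, state the correlation and its source and recompute.

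This edits one sentence in each document, plus the NT-proBNP scale reconciliation. It needs no extra patients or data and leaves the sample size unchanged. The cost is a lower stated power for LVEF and possibly none for NT-proBNP.
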